- Clinical status assessed using ordinal scale on Study Days 1, 3, 5, 8, 11, 15, 22, and 29;
- Change in clinical status using change in ordinal scale from Study Day 1 to Study Days 3, 5, 8, 11, 15, 22, and 29;
- Days of supplemental oxygen or worse (i.e., ordinal score of 5, 6, 7, 8) up to and including Study Day 29;
- Days of non-invasive ventilation/high-flow oxygen or worse (i.e., ordinal score of 6, 7, 8) up to and including Study Day 29;
- Whether a subject who has a baseline ordinal score of 5 requires new non-invasive oxygen use or worse (i.e., ordinal score of 6, 7, 8) during the study up to and including Study Day 29 (incidence);
- Days a subject who has a baseline ordinal score of 5 has an ordinal score of 6 or greater up to and including Study Day 29;
- Days of invasive mechanical ventilation/ECMO or worse (i.e., an ordinal score of 7 or 8) up to and including Study Day 29;
- Whether subject who has a baseline ordinal score of 5 or 6 requires new invasive ECMO use or worse (i.e., ordinal score of 7 or 8) during study up to and including Study Day 29 (incidence);
- Days a subject who has a baseline ordinal score of 5 or 6 has an ordinal score > 6 up to and including Study Day 29;
- Whether a subject is alive and without respiratory failure (ordinal score < 7) at Study Day 29;
- Time (days) to ventilation or death from Study Day 1 up to and including first 29 days of being on study.
- Days of hospitalization from date of admission up to and including Study Day 29.
- Values of C-reactive protein (CRP), ferritin, D-dimer, lactate dehydrogenase (LDH), and fibrinogen on Study Days 1, 3, 5, 8, and 11 (while hospitalized); and Study Days 15 and 29 (if attends in-person visit or still hospitalized).

Safety

- Whether a subject died from Day 1 up to and including Study Day 15.
- Whether a subject died from Day 1 up to and including Study Day 29.
- Whether a subject died from Day 1 up to and including Study Day 60.
- Time (days) to death from Study Day 1 up to and including Study Day 29.

- Whether a subject experienced at least one SAE up to and including Study Day 60.
- Whether a subject experienced at least one Grade 3 or Grade 4 AE up to and including Study Day 60.
- Episodes of early discontinuation or interruption of study product administration.

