	Subgroup	Repeat the primary analysis for this endpoint within each of the following subgroups: 
 Actual baseline ordinal score Baseline steroid use Baseline use of emerging COVID-19 treatments Duration of symptoms prior to enrollment (only using the \leq Median; $>$ Median classification)
9. Incidence of new invasive ECMO use through study Day 29 for subjects with baseline clinical status of 5 or 6;	Primary	
 No covariate adjustment
10. Days a subject who has a baseline clinical status of 5 or 6 has a clinical status > 6 up to and including Study Day 29;	Primary	
 No covariate adjustment
	Subgroup	Repeat the primary analysis for this endpoint within each of the following subgroups: 
 Actual baseline ordinal score Baseline steroid use Baseline use of emerging COVID-19 treatment Duration of symptoms prior to enrollment (only using the \leq Median; $>$ Median classification)
11. Proportion of subjects alive and without respiratory failure at Study Day 29;	Primary	
 No covariate adjustment
12. Time (days) to death or ventilation up to and Including Day 29	Primary	Adjust for the following covariates: 
 Baseline dexamethasone use Actual baseline ordinal score Baseline CRP value (Continuous) Age (continuous)

Endpoint	Analysis	Covariates/Subgroups
13. Days of hospitalization from date of admission by Study Day 29.	Primary	
 No covariate adjustment for this analysis
	Subgroup	Repeat the primary analysis for this endpoint within each of the following subgroups: 
 Actual baseline ordinal score Baseline steroid use Baseline use of emerging COVID-19 treatment Duration of symptoms prior to enrollment (only using the <= Median; > Median classification)
Other Secondary Endpoints: Safety		
1. Values of CRP ferritin, D-dimer, LDH, and fibrinogen on Study Day 1: Study Days 3, 5, 8, 11,15 and 29	Primary	
 No covariate adjustment
2. 14-day Mortality	Primary	1. Adjust for the following covariates: 
 Actual baseline ordinal score Baseline steroid use
3. 28-day Mortality	Primary	1. Adjust for the following covariates: 
 Actual baseline ordinal score Baseline steroid use

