13. Days of hospitalization from date of admission by Study Day 29.	Primary	
 If a subject is discharged and no further hospitalization data are available, consider the subject as not readmitted, no additional imputed days will be added. If a subject dies while hospitalized, the number of days of hospitalization will be imputed as the number of days between the date of admission and the expected date of subject's Study Day 29 visit+1.
	Subgroup	
 Use complete data for ordinal score to define this endpoint.

Endpoint	Analysis	Imputation Method
Other Secondary Endpoints: Safety		
1. Values of CRP, ferritin, D-dimer, LDH, and fibrinogen on Study Day 1: Study Days 3, 5, 8, 11,15 and 29	Primary	
 If results are not available for any visit day(s) but are available for visits before or after that visit, the average of the two nearest visits will be imputed for all missing visits between them. If a subject dies or is otherwise terminated early from the study, their last available observation will be carried forward. If baseline is missing, another pre-treatment dose will be used, or the earliest post treatment dose will be used.
2. 14-day Mortality	Primary	
 Subjects whose last assessment in the study is before Day 13 (beginning of Day 29 window) and before death will be considered not dead and censored at the date of their last observed assessment. Subjects who complete follow-up will be censored at Day 15. Deaths that occur after Day 15 will be censored at Day 15.
	Primary with Sensitivity Imputation	
 Subjects whose last assessment in the study is before Day 13 (beginning of Day 15 window) and were discharged to a location other than LTAC, hospice care or other hospital, or subjects died after Day 15 will be considered non-events and censored at Day 15. Subjects whose last assessment in the study is before Day 13 (beginning of Day 15 window) and before death and without being discharged to a location other than LTAC, hospice care or other hospital at their last assessment will be considered non-events and censored at the date of their last observed assessment. Subjects who complete follow-up will be censored at Day 15.

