The time to mechanical ventilation or death up to and including Day 29 will be defined as the elapsed time (in days) from Study Day 1 to date of mechanical ventilation or death. Any subjects whose last assessment is prior to obtaining the event and prior to Day 26 (beginning of Day 29 window) will be censored at the date of their last observed assessment. For the sensitivity analysis of this endpoint, subjects whose last assessment is

prior to obtaining the event and who were discharged to a location other than LTAC, hospice care, or other hospital will be considered recovered and censored at Day 29. For both primary and sensitivity analysis of this endpoint, subjects who complete follow-up will be censored Day 29. Events that occur after Day 29 will be censored at Day 29. A table will present median time to event along with corresponding 95% and 80% confidence intervals for each treatment along with the hazard ratio estimate and score test p-value from a Cox-proportional hazard model (Table 42). The Cox model will include as covariates baseline ordinal score, baseline CRP value, continuous age, and baseline dexamethasone use. Differences in time-to-event endpoints by treatment will be summarized with Kaplan-Meier curves (Figure 11). Analyses will be performed on the mITT population for those subjects who at baseline have an ordinal score of 5 or 6, CRP<150 mg/L, and age<85 years and results will be reported in Table 42. This analysis will be repeated for all subjects in the mITT population and results will be reported in Table 43.

Refer to Table 6 for a list of covariates and subgroup analyses for this endpoint. Refer to Table 7 for imputation methods to be applied to this endpoint.

Hospitalization

Duration (in days) of hospitalization will be defined as the number of days subject is hospitalized for COVID-19-related reasons starting from the date of randomization. It will be calculated as the total number of days hospitalized, including readmissions for COVID-19-related reasons. It will also be calculated as the total number of days hospitalized, including any readmissions regardless of cause. See Section 6.5 for the plan for handling subjects who do not have data through Day 29 or die prior to Day 29.

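### SAP 8.2.2 counts hospital days from randomization, but Section 3.2, Table 6 and the Table 7 in-hospital death rule count from admission; one origin is needed for all subjects.

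*SAP*

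**What the plan says.** The SAP gives two starting points for one endpoint.

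- **Section 8.2.2, Hospitalization:** duration "will be defined as the number of days subject is hospitalized for COVID-19-related reasons starting from the date of randomization". For incomplete follow-up and deaths it adds "See Section 6.5 for the plan for handling subjects who do not have data through Day 29 or die prior to Day 29".
- **Section 3.2, other secondary endpoints:** "Days of hospitalization from date of admission up to and including Study Day 29".
- **Table 6, row 13:** "Days of hospitalization from date of admission by Study Day 29". Table 7 row 13 carries the same label.
- **Table 7, row 13, in-hospital deaths:** the value is imputed as "the number of days between the date of admission and the expected date of subject's Study Day 29 visit+1".
- **Table 7, row 13, subjects discharged with no further hospital data:** "consider the subject as not readmitted, no additional imputed days will be added". This rule names no origin.

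Section 4.5 says that duration is taken from admission and discharge dates. The protocol's Table 3 asks for hospital days up to Day 29 and names no origin. Section 3.3.1 defines Study Day 1 as the first-dose date, or the randomization date for untreated subjects. The summaries of changes in SAP Section 15 do not address the point.

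**The concern.** A programmer who takes the definition from Section 8.2.2 and follows its cross-reference for deaths builds one variable on two clocks. A death then carries extra days that reflect only how long the subject had been in hospital before entering the trial. A programmer who starts from Section 3.2 builds a different variable, in which every subject carries those days.

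The two programmers would report different medians from the same data. Days before randomization cannot be changed by treatment, so including them adds variation unrelated to the comparison.

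**Working it through.** **Inputs.** The origins are those quoted from Sections 3.2 and 8.2.2 and from Tables 6 and 7. Subjects are already admitted at entry (protocol Section 5.1), and no criterion limits time since admission. Let a be the days from admission to Study Day 1. The documents give no distribution for a, so the values below are assumptions. First dose is taken to be on the day of randomization.

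**Formulas.**

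- Survivor in hospital through Day 29, Section 8.2.2: Day 1 to Day 29 inclusive = 29.
- Same survivor, Section 3.2: 29 + a.
- In-hospital death, Table 7: date difference from admission to Day 29 is 28 + a, and the rule's +1 makes it 29 + a.

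| a | Survivor, 8.2.2 | Survivor, 3.2 | Death, Table 7 | Gap if 8.2.2 governs survivors | Gap if 3.2 governs |
|---|---|---|---|---|---|
| 0 | 29 | 29 | 29 | 0 | 0 |
| 1 | 29 | 30 | 30 | 1 | 0 |
| 4 | 29 | 33 | 33 | 4 | 0 |
| 7 | 29 | 36 | 36 | 7 | 0 |

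For a = 4 the death value is 28 + 4 + 1 = 33, so the 33 already includes Table 7's +1.

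**Effect on the planned summary.** Section 8.2.2 plans medians and quartiles by treatment. As an illustration only, 200,000 subjects were simulated for each death rate. Survivor stay was lognormal (median 8 days, log-SD 0.7), rounded up and capped at 29; a was Poisson with mean 3; all deaths were treated as in-hospital. Every one of these inputs is assumed.

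| Deaths | Mixed origins: Q1/median/Q3 (mean) | All from randomization | All from admission |
|---|---|---|---|
| 5% | 6/9/15 (11.45) | 6/9/15 (11.30) | 9/12/18 (14.30) |
| 15% | 6/10/19 (13.59) | 6/10/19 (13.14) | 9/13/22 (16.14) |
| 30% | 7/12/30 (16.84) | 7/12/29 (15.94) | 10/16/31 (18.94) |

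Mixing origins leaves the quartiles unchanged at 5% and 15% deaths and moves only Q3, by one day, at 30%. The reason is that in-hospital deaths sit at or above every survivor under either origin. Choosing admission over randomization for everyone moves each quartile by 2 to 4 days, about the assumed mean of a. Means are more exposed to mixing: at 15% deaths the difference is 13.59 − 13.14 = 0.45 days.

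**The case against.** The strongest reply is that Section 8.2.2 is one stray phrase. Section 3.2, both table labels and the death rule all say admission, Section 4.5 uses admission dates, and Section 8.2.2 itself points to Tables 6 and 7. On that reading deaths and survivors share an origin. This stands as a possible reading, so the split between deaths and survivors depends on Section 8.2.2 governing survivors. It does not remove the conflict, because nothing says which section prevails and Section 8.2.2 is where the analysis is defined.

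A second reply is that a worst-outcome rule may properly place deaths above survivors. That is fair as to order. But the excess here equals each subject's stay before the trial, so it differs between deaths and is not a chosen penalty.

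A reader might infer that formal testing is at stake because Table 9 lists the endpoint for the global analysis. The documents do not support that as a commitment. Section 6.8 makes those analyses optional, and the Table 44 and 45 shells have no row for hospital days. The shell that Table 39 follows (Table 36) has no p-value, and Section 8.2.2 has Figure 22 show deaths with imputed days as a separate group.

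A reader might also take the allowance of up to four prior remdesivir doses (exclusion begins at five) as evidence of four-day stays before entry. Doses do not measure time since admission, and four once-daily doses can span a date difference of three days. They show only that earlier admission is possible.

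**Conclusion.** The conflict is real and unreconciled, and it should be corrected. As written, Section 8.2.2 with Table 7 gives an in-hospital death a days more than a survivor who never leaves hospital. Under Section 3.2 the gap is zero, but Section 8.2.2 is then wrong and all values include time before randomization.

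The practical effect is limited. This is an other secondary endpoint reported by medians and quartiles. In the illustration, mixing origins barely moved those figures, although the maximum in the Table 39 shell could change. The larger exposure is the undecided choice of origin, which shifts all quantiles by about a. The stronger statement, that the plan definitely measures deaths and survivors from different origins, is not established, because it holds only on the Section 8.2.2 reading.

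The sizes rest on an assumed a and on dosing on the day of randomization.

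**What to change.** State one origin in Sections 3.2 and 8.2.2, Table 6 row 13 and Table 7 row 13, and apply it to deaths and survivors alike. Study Day 1 as defined in Section 3.3.1, counted through Study Day 29, is preferable. It excludes time before treatment and matches the SAP's other day-count endpoints. Assign in-hospital deaths the maximum on that scale, 29 days.

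Naming randomization as the origin would leave a loose end. A subject dosed the day after randomization and never discharged would have 30 days from randomization through Study Day 29, so a death set to 29 would rank below that survivor. Using admission throughout would also end the contradiction, but it keeps the days that treatment cannot affect.

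In the same edit, align the subgroup line of Table 7 row 13, which derives the endpoint from ordinal-score data, with the chosen definition. The cost is SAP wording and the matching derivation in the program. No data collection changes.

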8.3. Exploratory Efficacy Analyses

Key Concomitant COVID-19 Treatments

The post-baseline usage, onset, and duration of treatment of key concomitant COVID-19 treatments will be summarized by treatment for each concomitant medication/therapy category (Table 78). If no concomitant COVID-19 treatment has been applied up to Study Day 60, day of onset will be censored at Study Day 60 for descriptive statistics (means, medians). Duration will be defined as the number of days between day of onset and end of medication. For ongoing medication at the end of the study, the medication end date will be imputed based on rules in Table 8.

Steroid Usage

Steroid usage and steroid type for indications other than COVID-19 post-baseline will be summarized by treatment group (Table 87). If no concomitant COVID-19 treatment has been applied up to Study Day 60, day of onset will be censored at Study Day 60 for descriptive statistics (means, medians). Duration will be defined as the number of days between day of onset and end of medication. For ongoing medication at the end of the study, the medication end date will be imputed based on rules in Table 8.

Details of analyses for virology and markers of inflammation and immune response will be covered in a separate SAP.

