² Screening laboratory tests include: ALT, AST, creatinine (and calculate an estimated glomerular filtration rate (eGFR) the formula used is determined by the sites, but should be consistent throughout the study), and urine or serum pregnancy test for females of child-bearing potential. Laboratory tests performed as part of routine clinical care in the 48 hours prior to enrollment will be accepted for determination of eligibility.

³ Baseline assessments should be performed prior to first infusion. Laboratory tests performed as part of routine clinical care in the 24 hours prior to first dose will be accepted for the baseline safety laboratory tests. Baseline may be the same as the screening laboratory tests if obtained in the 24 hours prior to first dose.

⁴ Safety laboratory tests include WBC with differential, hemoglobin, platelets, creatinine, total bilirubin, ALT, AST, and INR.

⁵ Any laboratory tests performed as part of routine clinical care within the specified visit window can be used for safety laboratory testing. ⁶ In-person visits are preferred but recognizing quarantine and other factors may limit the subject's ability to return to the site for the visit. In this case, the visit may be performed by phone.

- If still hospitalized at Day 15 and 29 or returns for an in-person visit: assess adverse events, collect clinical data, vital signs, safety laboratory tests, and research laboratory samples (OP swab and blood) as able.
- If phone call only on Days 15 and 29 and all Day 22 and Day 60 visits: assess adverse events, clinical status (ordinal scale), readmission to a hospital, and mortality only.

⁷ Oropharyngeal swabs are preferred, but if these are not obtainable, saliva or nasopharyngeal or nasal swabs may be substituted. ⁸ Pre-dose serum sample collections for PK and immunogenicity.

⁹ To include markers of inflammation and coagulation: CRP, ferritin, fibrinogen, d-dimer.

¹⁰ Day 8, 22 and 60 visits performed by phone call or home visit if discharged from the site hospital: assess adverse events, clinical status (ordinal scale), readmission to a hospital, and mortality only.

¹¹ Only collected at selected sites capable of processing.

¹² Steroids and other concomitant therapies intended as specific treatment of COVID-19, as well as all biologics, will be assessed from 7 days prior to enrollment to Day 29. All other concomitant medications will be assessed from 7 days prior to enrollment to Day 15 or upon discharge, whichever comes first.

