 To evaluate the virologic efficacy of risankizumab as compared to the control arm as assessed by: Percent of subjects with SARS-CoV-2 detectable in saliva (or best technology) sample at Days 3, 5, 8, 11, 15, and 29. Quantitative SARS-CoV-2 virus in saliva (or best technology) sample at Days 3, 5, 8, 11, 15, and 29. Quantitative SARS-CoV-2 virus in blood at Days 3, 5, 8, and 11. 	 Qualitative and quantitative polymerase chain reaction (PCR) for SARS-CoV-2 in OP swab on Day 1; Days 3, 5, 8, and 11 (while hospitalized); and Days 15 and 29 (if attends in-person visit or still hospitalized). Qualitative and quantitative PCR for SARS-CoV-2 in blood on Day 1; Days 3, 5, 8, and 11 (while hospitalized). 		
2. To evaluate the impact of study interventions on markers of inflammation and immune response.	 Proteomic analysis of plasma cytokines and markers of inflammation including IL-17A, IL-22 and IL-1b. Transcription, epigenetic, and molecular profiles of mRNA in peripheral blood mononuclear cells (PBMC). Phenotypic and responsiveness markers in PBMC. 		
3. To evaluate post-baseline usage of key concomitant COVID-19 treatments (e.g., steroids) in investigational therapeutic arms as compared to the control arm.	• Use of concomitant COVID-19 treatments up to Day 29.		

	OBJECTIVES		ENDPOINTS (OUTCOME MEASURES)
Stage-specific objective/endpoint	4. To evaluate risankizumab pharmacokinetics (PK) and immunogenicity in subjects with COVID-19.	•	Serum samples for PK (at pre-dose, Day 5, Day 15, and Day 29) and serum samples for anti-drug antibodies and neutralizing antibodies at pre-dose and Day 29.

** "New or increased" is relative to pre-COVID status

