6.5 Concomitant Therapy

6.5.1 Permitted Concomitant Therapy and Procedures

For patients that are eligible for the study, other therapy received prior to enrollment with any other experimental treatment or off-label use of marketed medications that are intended as specific treatment for COVID-19 or the SARS-CoV-2 infection (i.e., post-exposure prophylaxis [PEP]) are permitted but must be discontinued on enrollment. There is no waiting period between discontinuation of these treatments and administration of study products. However, these prior treatments and their end date should be documented on the concomitant medication form in the EDC system.

Steroids for the treatment of COVID-19 may be used per the local institution's written standard of care (i.e., not just an individual clinician decision) or NIH COVID-19 Treatment Guidelines (https://www.covid19treatmentguidelines.nih.gov/). NIH COVID-19 Treatment Guidelines provide current evidence-based information about the optimal management of COVID-19. NIH COVID-19 Treatment Guidelines were updated on June 25, 2020 to include a Grade AI recommendation for using dexamethasone (6 mg per day for up to 10 days) in patients with COVID-19 who are mechanically ventilated and a Grade B1 recommendation for patients with COVID-19 who require supplemental oxygen but who are not mechanically ventilated based on preliminary data from the RECOVERY trial. The NIH Guidelines also recommend against using dexamethasone in COVID-19 patients who do not require supplemental oxygen.

Steroid regimens for other standard indications including asthma exacerbation, ARDS, COPD, laryngeal edema, adrenal insufficiency, shock, etc. are allowable up to a maximum of prednisone 60 mg daily or equivalent. All steroid use regardless of indication until Day 29 will be recorded in the EDC system.

Subjects who are taking another antiviral for a concurrent infection (e.g. oseltamivir for an influenza virus) or another existing medical condition (e.g. hydroxychloroquine for lupus) may

continue with the treatment. Note that these treatments may be thought of as an off-label medication for COVID-19, however, because they were being used prior to study enrollment for another indication, they are allowable.

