Outpatient experimental treatment or off-label use of marketed medications that are intended as specific treatment for COVID-19 do not need to be discontinued if there is a written policy or guideline for the local standard of care and treatment of COVID-19 patients or SARS-CoV-2 infection (i.e., not just an individual clinician decision). In the absence of a local written standard of care, the National Institutes of Health (NIH) COVID-19 Treatment Guidelines may be used. If concomitant medications are used, there should be plans on how the concomitant drugs are stopped in case of additive toxicities.

Steroids and other concomitant therapies intended as specific treatment of COVID-19, as well as all biologics, will be assessed from 7 days prior to enrollment to Day 29. All other concomitant medications will be assessed from 7 days prior to enrollment to Day 15 or upon discharge, whichever comes first. All prescription medications should be recorded during this time period with the exceptions listed in the bullets below. All medications, except biologics, convalescent plasma and corticosteroids, can be recorded once regardless of the number of times it was given during the time period. For example, vasopressors should be recorded when first dose given (as the start date) and the last dose given (as the end date) during the period of assessment.

Sites do not need to record any of the following categories of medications as concomitant medications:

- All topical medications: ointments, creams, and lotions;
- All intranasal medications: nasal decongestants, nasal allergy medications, nasal steroids, and nasal saline drops/sprays;
- All ophthalmic medications: ophthalmic allergy medication, ophthalmic medications for infection, and ophthalmic medications for eye dryness (e.g., saline eye drops);
- Antiseptic mouth wash, lozenges;
- Cough medication: mucolytics, cough suppressants, and expectorates;
- GI medications: H2 blockers, proton pump inhibitors, GI stimulants, prokinetics, laxatives, stool softeners, antacids, anti-diarrheal and anti-nausea medications;
- Insulin and medications for diabetic control;
- Symptomatic care medications: antipyretics, antihistamines, decongestants, and NSAIDs;
- Vitamins, minerals or herbal supplements, dietary supplements, iron/ferrous sulfate, magnesium, calcium, electrolyte replacement;
- Albumin infusions;
- Melatonin;
- Nicotine patch, lozenge, gum, or nasal spray, or other product to treat tobacco dependence;

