- Values of WBC with differential, hemoglobin, platelets, creatinine, eGFR, total bilirubin, ALT, AST, and INR on Study Days 1, 3, 5, 8, and 11 (while hospitalized); and Study Days 15 and 29 (if attends in-person visit or still hospitalized).

Exploratory Endpoints

The exploratory endpoints are:

- Whether a subject used concomitant COVID-19 treatments (e.g., steroids) post-baseline up to and including Study Day 29.

Details for the exploratory endpoints listed below are not provided in this master SAP will be provided in a separate SAP addendum and reported in a separate CSR addendum.

- Whether a subject has detectable SARS-CoV-2 according to polymerase chain reaction (PCR) in saliva from oropharyngeal (OP) swab (or best technology) on Study Day 1; Study Days 3, 5, 8, and 11 (while hospitalized); and Study Days 15, and 29 (if subject attends in-person visits or is still hospitalized);
- Quantitative polymerase chain reaction (PCR) for SARS-CoV-2 in saliva from OP swab on Study Days 1, 3, 5, 8, and 11 (while hospitalized); and Study Days 15 and 29 (if subject attends in-person visit or is still hospitalized);
- Whether a subject has detectable SARS-CoV-2 in blood at Study Days 1, 3, 5, 8, and 11 (while hospitalized);
- Quantitative PCR for SARS-CoV-2 in blood on Study Days 1, 3, 5, 8, and 11 (while hospitalized);
- Proteomic analysis of plasma cytokines and markers of inflammation;
- Transcription, epigenetic, and molecular profiles of mRNA in peripheral blood mononuclear cells (PBMC);
- Phenotypic and responsiveness markers in PBMC.

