Concomitant COVID-19 Treatments are defined as medications that started before dose 1 of study product and continued throughout the study or those started after a subject took study product.

SD=Standard Deviation. Min=Minimum. Max=Maximum.

N=Number of subjects in the Safety population.

n=Number of subjects reporting at least one of the concomitant COVID-19 treatments. Refer to Section 6.4 for a list of COVID-19 treatments of interest.

^a Study day onset is defined as the start day of the concomitant medication.

Table 87: Summary of Steroid Usage for Indications Other than COVID-19 by Treatment of Indication — Safety Population

Type	Summary Measure	Treatment A (N=X)						Treatment B (N=X)					
		n	Mean	SD	Median	Min	Max	n	Mean	SD	Median	Min	Max
[COVID-19 Treatment 1]	Number of Subjects	x	-	-	-	-		x	-	-	-	-	-
	Study Day Onset ^a	x	x.x	x.xx	x.x	x	x	x	x.x	x.xx	x.x	x	x
	Duration (days)	x	x.x	x.xx	x.x	x	x	x	x.x	x.xx	x.x	x	x

Concomitant Steroid Treatments are defined as steroids for indications other than COVID-19 that started before dose 1 of study product and continued throughout the study or those started after a subject took study product.
SD=Standard Deviation. Min=Minimum. Max=Maximum.
N=Number of subjects in the Safety population.
n=Number of subjects reporting steroid usage for indications other than COVID-19. Refer to Section 6.4 for a list of steroids of interest.
^a Study day onset is defined as the start day of the concomitant medication.

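### SAP 8.3 enters Day 60 as the onset day for subjects who never used a concomitant COVID-19 treatment, although collection ends at Day 29 and the table shell describes users only

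*SAP*

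**What the plan says.** SAP 8.3 plans to summarise usage, onset and duration of key concomitant COVID-19 treatments by arm and medication category. For non-users it adds: "If no concomitant COVID-19 treatment has been applied up to Study Day 60", the "day of onset will be censored at Study Day 60 for descriptive statistics (means, medians"). The next paragraph, on steroids given for indications other than COVID-19, repeats the same sentence.

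Other parts of the plan use a different horizon or a different set of subjects:

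- **Collection.** Protocol 1.2 (Table 1, footnote 12) says that steroids, other COVID-19 therapies and biologics "will be assessed from 7 days prior to enrollment to Day 29". Protocol 6.5.1 agrees ("as well as all biologics, will be assessed from 7 days prior to enrollment to Day 29") and adds for steroids: "All steroid use regardless of indication until Day 29 will be recorded in the EDC system". The SAP's own schedule (Table 10, footnote 12) gives the same limit.
- **Endpoint.** Protocol Table 3: "Use of concomitant COVID-19 treatments up to Day 29". SAP 3.2: "Whether a subject used concomitant COVID-19 treatments (e.g., steroids) post-baseline up to and including Study Day 29". SAP Tables 6 and 7 carry the same Day 29 limit.
- **Table shell.** SAP Table 86 defines n as: "Number of subjects reporting at least one of the concomitant COVID-19 treatments". Its footnote takes onset as the day the medication started and mentions no Day 60 value.
- **Missing data.** SAP Table 7 allows no imputation for this endpoint, apart from the partial-date rules in Table 8.

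**The concern.** A censoring day is not an onset day. Once 60 is averaged with real start days, the mean stops describing when treatment began and starts describing how many subjects were never treated. Section 8.3 presents usage and onset as separate summaries, so a reader could take a difference in frequency of use for a difference in timing.

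The chosen value also lies outside the observed period. With collection ending at Day 29, the condition of no treatment up to Day 60 cannot be verified, and the planned collection yields no onsets on Days 30 to 60. As worded, the rule would also give Day 60 to an untreated subject who died or left the study early.

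Finally, a programmer working from the text of 8.3 and one working from the Table 86 shell would report different onset summaries from the same data.

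**Working it through.** The documents state no use rate, expected onset day or result that depends on this rule, so there is no planned figure to reproduce. The inputs below, other than the fill value of 60 and the collection limit of 29, are assumptions shown over a range. The rule is applied within a medication category.

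**Mean.** Let p be the share of users, m the mean onset day among users and C the value entered for non-users. Then

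reported mean = p × m + (1 − p) × C.

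With m = 5:

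| Share of users | C = 60 (SAP 8.3) | C = 29 | Users only |
|---|---|---|---|
| 10% | 54.5 | 26.6 | 5.0 |
| 25% | 46.25 | 23.0 | 5.0 |
| 50% | 32.5 | 17.0 | 5.0 |
| 75% | 18.75 | 11.0 | 5.0 |
| 90% | 10.5 | 7.4 | 5.0 |

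**Effect of a difference in use alone.** With the same m in both arms, a 10-point difference in use shifts the mean by 0.10 × (C − m).

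- C = 60: 0.10 × 55 = 5.5 days for m = 5; 0.10 × 57 = 5.7 for m = 3; 0.10 × 50 = 5.0 for m = 10.
- C = 29: 2.4, 2.6 and 1.9 days respectively. A Day 29 fill roughly halves the artefact but does not remove it.

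The shift does not depend on the level of use. For m = 5 and C = 60:

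- 30% against 20% users gives 0.3 × 5 + 0.7 × 60 = 43.5 and 0.2 × 5 + 0.8 × 60 = 49.0.
- 90% against 80% gives 0.9 × 5 + 0.1 × 60 = 10.5 and 0.8 × 5 + 0.2 × 60 = 16.0.

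Both pairs differ by 5.5 days.

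**Effect of a real difference in timing.** A 2-day delay among users moves the mean by 2p: 0.2 days at p = 10% and 1.8 days at p = 90%. For m = 5, that equals a change in use of 0.2/55 = 0.4 points and 1.8/55 = 3.3 points.

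**Share of variance due to user status.** This is p(1 − p)(C − m)² / [p(1 − p)(C − m)² + p × V], where V is the variance of onset among users. With user onset uniform on Days 1–5, 1–15 or 1–29 and p from 5% to 95%, it runs from 59% to 99.9%, and is at least 93% when about half or fewer are users.

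**Median.** When p is below 50%, the median is 60 whatever the timing. Above 50% it is the 0.5/p quantile of user onset. With onset uniform on Days 1–15 (users-only median 8) it is 15 at p = 51%, 13 at 60%, 10 at 75%, 9 at 90% and 8 at 95%. These values are the same for a Day 29 fill.

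**Reading the rule as true censoring.** If every non-user is censored at Day 60, the Kaplan-Meier restricted mean to Day 60 is the mean of the smaller of onset and 60, which is again p × m + (1 − p) × 60. That reading gives the same number.

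**The case against.** The best defence is that the SAP does not settle that non-users enter the summary. The Table 86 shell and Table 7 both point to users only, and a programmer following the shell would already produce the right table. That stands in part: the distortion follows from the text of 8.3, not from every reading of the plan. But 8.3 is an explicit instruction, and nothing in the plan says that the shell overrides it.

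Three stronger readings might be inferred, and the documents do not support them.

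- *The median also mostly measures non-use.* It is uninformative only where fewer than half are users. That is plausible for categories whose drugs Protocol 6.5.2 prohibits. It is not clear for corticosteroids: every eligible subject needs oxygen or ventilation, and Protocol 6.5.1 permits steroids under local standards or guidelines. With majority use the median is a real onset day, although it still moves somewhat with the share of users.
- *This summary is the planned answer to the objective on concomitant treatment.* The objective concerns use, and the SAP endpoint is whether a subject used such treatment. Table 86 has its own row for number of subjects, so a difference in frequency would be visible beside the onset row.
- *The comparison concerns rescue therapy.* Protocol 6.5.3 marks rescue medicine as not applicable.

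A further fair point is that onset among users conditions on something that happens after randomisation. It is suitable as description, not as a randomised comparison of timing.

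**Conclusion.** Section 8.3 is wrong as written and must be reconciled with the Day 29 collection limit, the Day 29 endpoint, Table 86 and Table 7. If followed, it yields a mean onset day driven mainly by the share of non-users: 5.0 to 5.7 days per 10 points of use, for assumed mean user onset of Day 10 to Day 3. The direction does not depend on those assumptions; the size does. The claim about distortion is limited to the mean. The median carries no timing information below 50% use and is a genuine onset quantile above it.

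The steroid paragraph has a separate error. It covers steroids for other indications, but its trigger is the absence of COVID-19 treatment. The reference in 8.3 to Table 78 is also wrong, since that table reports hemoglobin.

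The consequence is small: an exploratory, descriptive summary with no bearing on the primary analysis, the error rate or the sample size.

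**What to change.** 1. Delete the Day 60 sentence from both paragraphs of SAP 8.3. This also removes the wrong trigger in the steroid paragraph.
2. State that number and percent of users through Day 29 will be reported by arm and category, with onset day and duration described among users only. This matches the shells of Tables 86 and 87; only the percent is new.
3. Change the reference to Table 78 in 8.3 to Table 86.
4. If time to first use is wanted, specify a cumulative incidence curve through Day 29, with death as a competing event and censoring at last assessment. A plain Kaplan-Meier curve that censors deaths would ignore that death prevents later treatment.

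The cost is a few sentences of SAP text and one added percentage in each shell. No new data are needed.
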